9.4.3 Safety Analyses

Adverse events will be coded as previously described and Section 8. Safety analyses will be reported and presented as summary statistics. For side effects, descriptive statistics and Fisher's exact tests will be performed for possible differences between the treatment arms.

9.4.4 Baseline Descriptive Statistics

All demographics will be summarized using mean \pm SD, for continuous variables and frequencies and percentages for categorical variables. Standard statistical tests (chi-square and 2-sample t-tests or Wilcoxon rank-sum test) will be performed to examine whether patients differ with regard to demographics and other baseline variables in the 2 study arms.

9.4.5 Planned Interim Analyses

An interim analysis of the primary and secondary endpoints will be conducted after the enrollment of 30 patients, with 15 patients in each arm. This analysis will assess the data collected up to that point to ensure the study's integrity and to make any necessary adjustments based on the findings.

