9 STATISTICAL CONSIDERATIONS

9.1 Statistical Hypotheses

Primary endpoints:

- H_0 : Mean change in pain levels pre / post GNB = Mean change in pain levels pre / post conventional therapy
- H_1 : Mean change in pain levels pre / post GNB \neq Mean change in pain levels pre / post conventional therapy

Secondary endpoints:

- H_0 : Mean duration of analgesia for patients receiving GNB = Mean duration of analgesia for patients receiving conventional therapy
- H_1 : Mean duration of analgesia for patients receiving GNB \neq Mean duration of analgesia for patients receiving conventional therapy
- H_0 : Mean APS-POQ-RED score for patients receiving GNB = Mean APS-POQ-RED score for patients receiving conventional therapy
- H_1 : Mean APS-POQ-RED score for patients receiving GNB \neq Mean APS-POQ-RED score for patients receiving conventional therapy
- H_0 : Mean ED LOS for patients receiving GNB = Mean patient satisfaction for patients receiving conventional therapy
- H_1 : Mean ED LOS for patients receiving GNB \neq Mean patient satisfaction for patients receiving conventional therapy

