9.2 Sample Size Determination

To determine the number of patients needed in each study arm for sufficient sample size we considered the primary outcome of change in pain levels pre/post treatment as measured by the NRS as this was the largest sample size needed to detect a clinically meaningful effect.

The sample size was loosely based on an RCT by [Shanahan et al. 2023](#), for which the mean change in the visual analog scale (VAS: 0-10 scale) from baseline at 2 weeks was 3.5 (GNB) and 0.7 (sham injection group). Assuming the mean change in NRS pain score pre/post treatment between the GNB and standard analgesia (difference in difference) will be smaller in a shorter period of time, group sample size of 17 (each group) will achieve 80% power to detect a difference in NRS between treatment arms as small as 1.6, with alpha set at 0.05 and standard deviation of differences set at 2.0 using a two-sided two-sample equal-variance t-test with a 5-10% loss to follow-up at the 24 hour mark.

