This study may be temporarily suspended or prematurely terminated by the Sponsor or the PI at any site if there is sufficient reasonable cause. Written notification, documenting the reason for study suspension or termination, will be provided by the suspending or terminating party to the investigator. If the study is prematurely terminated or suspended, the Principal Investigator (PI) will promptly inform study participants, the Institutional Review Board (IRB), and sponsor and will provide the reason(s) for the termination or suspension. Study participants will be contacted, as applicable, and be informed of changes to the study visit schedule.

Circumstances that may warrant termination or suspension include, but are not limited to:

- Determination of unexpected, significant, or unacceptable risk to participants
- Demonstration of efficacy that would warrant stopping
- Insufficient compliance to protocol requirements
- Data that are not sufficiently complete and/or evaluable
- Determination that the primary endpoint has been met
- Determination of futility

Study may resume once concerns about safety, protocol compliance, and data quality are addressed, and satisfy the sponsor, IRB and/or Food and Drug Administration (FDA).

In terminating the study, the Sponsor and the Principal Investigator will assure that adequate consideration is given to the protection of the subjects' interests.

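### The look at 30 of 34 patients permits unspecified changes driven by endpoint results and does not exclude an efficacy stop, while the trial is sized for a fixed test at 5%

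*Protocol*

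**What the plan says.** Protocol 9.4.5 commits to the look: "An interim analysis of the primary and secondary endpoints will be conducted after the enrollment of 30 patients, with 15 patients in each arm". It gives two purposes: to protect the integrity of the study, and "to make any necessary adjustments based on the findings". It does not say what may be adjusted, who decides, or whether results by arm may be the basis.

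Section 9.1 defines the endpoints concerned as comparisons between arms. For the primary endpoint the null hypothesis is "Mean change in pain levels pre / post GNB = Mean change in pain levels pre / post conventional therapy".

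Section 10.1.2 lists circumstances that may lead to suspension or termination. Two of them are "Demonstration of efficacy that would warrant stopping" and "Determination that the primary endpoint has been met". Neither carries a criterion, and the list neither refers to 9.4.5 nor excludes it.

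Section 9.2 states that a "group sample size of 17 (each group) will achieve 80% power", "with alpha set at 0.05", for a two-sided two-sample t-test. It makes no allowance for an interim look. The only multiplicity adjustment for the primary endpoint (9.4.1, Tukey-Kramer) concerns pairwise arm and time comparisons.

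Section 6.3 states that nobody is blinded. Section 10.1.5 places oversight with the principal investigator and the Division of Ultrasound and plans no data and safety monitoring board.

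**The concern.** An interim analysis costs no type I error when nothing is claimed and nothing is changed because of it. The difficulty is that 9.4.5 says the findings may lead to changes, and it names the primary and secondary endpoints as the source of those findings. Since 9.1 frames these endpoints as differences between arms, the natural reading is a comparison by arm. The text does not say so outright, so this is a reading.

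With 10.1.2 alongside, a team that finds p<0.05 at 30 patients could end the trial and remain within the protocol. A team that finds a non-significant result could enlarge the trial and also remain within it. In either case a final p-value read against 0.05 may no longer have a 5% error rate. No blinded or independent body stands between the interim result and those who treat the remaining patients and collect their pain scores.

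**Working it through.** **Inputs from the protocol.** Interim at 15 per arm (9.4.5); final at 17 per arm, two-sided t-test, alpha 0.05, difference 1.6, SD 2.0 (9.2).

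**Assumptions that are not in the protocol.** Normal data, equal arms, and every interim test level and extension rule below.

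**Step 1: the plan's own 5%.** In 1,000,000 simulated trials with no true difference, one t-test at 17 per arm rejects in 0.0501. The simulation standard error is √(0.05 × 0.95 / 1,000,000) = 0.0002. The plan's error rate is reproduced when there is a single test and nothing is changed.

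**Step 2: position of the look.** Information fraction 30/34 = 0.882. Correlation between the interim and final statistics ρ = √(30/34) = 0.939.

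**Step 3: an interim p<0.05 is claimed or ends the trial; otherwise a final test at 0.05.**

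P(|Z₁|>1.96 or |Z₂|>1.96) = 1 − ∫ φ(x)[Φ((1.96−ρx)/√(1−ρ²)) − Φ((−1.96−ρx)/√(1−ρ²))]dx, with x from −1.96 to 1.96. The result is 0.0660.

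The t-test simulation (15 then 17 per arm) gives 0.0663, made up as follows:
- final p<0.05: 0.0501
- interim p<0.05 but final p≥0.05: 0.0162
- sum: 0.0501 + 0.0162 = 0.0663

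Interim p<0.05 occurs in 0.0499 of null trials, so 0.0162/0.0499 = about one third of false interim successes would not be significant at 34 patients.

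**Step 4: no interim claim, but the sample size is changed.** As an example, take an extension to 26 per arm. With the 9.2 inputs, exact noncentral-t power is 0.807 at 26 per arm, which makes 26 a plausible target. One final test at 0.05 follows, at 26 per arm if extended and at 17 per arm if not:
- extend whenever interim p≥0.05: 0.0646
- extend only if 0.05≤p<0.20: 0.0530
- extend only if 0.05≤p<0.10: 0.0475

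The rule chosen decides the direction as well as the size.

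**Step 5: a claim at interim only at p<0.001, final test at 0.05.** Step 3 with 3.29 in place of 1.96 for Z₁ gives 0.0500; the simulation gives 0.0501.

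**Step 6: what the look can spare.** 34 − 30 = 4 patients at most.

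**The case against.** The strongest reply is that the inflation figures measure rules the protocol never states. Section 9.4.5 mentions no test level, no p-value trigger and no change of sample size, and an interim boundary could properly sit in a statistical analysis plan that is not shown. This stands. The 6.6% assumes that no such boundary exists, and the extension figures run from slightly below to above 5%. All of them are illustrations. A missing boundary is not the complaint. The complaint is the permission in the protocol itself, which a boundary for an efficacy test would not by itself limit.

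It is also fair that 10.1.2 is a general list and that 9.4.5 names integrity as a purpose. An efficacy stop at 30 patients follows only when two sections are read together that the protocol does not join. The protocol does not keep them apart either, so the stop is permitted but not planned.

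Four stronger readings are tempting and not supported:
- A reader might infer that the trial's type I error is 6.6%. The documents do not say that an interim p<0.05 will be claimed. If nothing is claimed or changed, the rate is 5.0%.
- A reader might add "Determination of futility" from 10.1.2 to the list of threats. Stopping for futility cannot raise type I error.
- A reader might take the bimonthly review in 10.1.6 as release of results by arm. The text describes a random check to verify data.
- A reader might count the power statement in 9.2 as part of this point. The 9.2 inputs give 0.619 at 17 per arm, not 80%, but that is a separate matter. The inputs are used here only to choose 26 per arm as an example.

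**Conclusion.** The point holds as a fault in what the protocol permits. Section 9.4.5 ties unspecified changes to endpoint findings at 88% of enrolment without excluding results by arm. Section 10.1.2 does not exclude an efficacy stop at that look, and 9.2 makes no allowance for either.

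The effect on type I error depends on what is done: none if the look changes nothing, about 1.6 percentage points if an interim p<0.05 is claimed or ends the trial, and between slightly below 5% and about 6.5% under the extension rules assumed here. These figures rest on normal data, equal arms and, for the 6.6%, no boundary in the unseen analysis plan. It also remains a reading that the interim analysis compares the arms.

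The inflation is modest. The change is still worth making before the 30-patient look, because the open-label setting has no independent monitoring and the look can spare so few patients.

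**What to change.** Reword 9.4.5 as a review of safety, data quality and recruitment with no efficacy comparison by arm. Remove the permission for adjustments as far as it concerns comparative results. State in 10.1.2 that the efficacy and endpoint-met grounds do not apply at this look.

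If an efficacy look is kept, limit it to the primary endpoint, allow an efficacy claim only at p<0.001 with the final test at 0.05 (overall 5.0%, step 5), and bar design changes based on results by arm.

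The cost is wording in two sections and the loss of an early stop worth at most four patients. Under the kept option little of that stop remains: with the 9.2 inputs, p<0.001 at 15 per arm has probability 0.096, an expected saving of 4 × 0.096 = 0.4 patients.

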9.4.6 Sub-Group Analyses

None.

9.4.7 Tabulation of Individual Participant Data

Individual patient data will be listed by endpoint of pain rating on NRS at either 1-hour after enrollment or at time of discharge from the ED (whichever occurs first), via pain questionnaire administered at that same time, and duration of analgesia (which will be assessed during a follow-up phone call performed by a research assistant) at 24 to 36 hours after enrollment.

9.4.8 Exploratory Analyses

None.

10 SUPPORTING DOCUMENTATION AND OPERATIONAL CONSIDERATIONS

10.1 Regulatory, Ethical, and Study Oversight Considerations

10.1.1 Informed Consent Process

10.1.1.1 Consent/Accent and Other Informational Documents Provided To Participants

Consent forms describing in detail the GNB, study procedures, and risks are given to the participant and written documentation of informed consent is required prior to starting intervention/administering GNB. The following consent materials are submitted with this protocol: **Informed Consent Form**.

10.1.1.2 *Consent Procedures and Documentation*

Informed consent is a process that is initiated prior to the individual's agreeing to participate in the study and continues throughout the individual's study participation. Consent forms will be Institutional Review Board (IRB)-approved and the participant will be asked to read and review the document. The investigator will explain the research study to the participant and answer any questions that may arise. A verbal explanation will be provided in terms suited to the participant's comprehension of the purposes, procedures, and potential risks of the study and of their rights as research participants. Participants will have the opportunity to carefully review the written consent form and ask questions prior to signing. The participants should have the opportunity to discuss the study with their family or surrogates or think about it prior to agreeing to participate. The participant will sign the informed consent document prior to any procedures being done specifically for the study. Participants must be informed that participation is voluntary and that they may withdraw from the study at any time, without prejudice. A copy of the informed consent document will be given to the participants for their records. The informed consent process will be conducted and documented in the source document (including the date), and the form signed, before the participant undergoes any study-specific procedures. The rights and welfare of the participants will be protected by emphasizing to them that the quality of their medical care will not be adversely affected if they decline to participate in this study.

10.1.2 *Study Discontinuation and Closure*

This study may be temporarily suspended or prematurely terminated by the Sponsor or the PI at any site if there is sufficient reasonable cause. Written notification, documenting the reason for study suspension or termination, will be provided by the suspending or terminating party to the investigator. If the study is prematurely terminated or suspended, the Principal Investigator (PI) will promptly inform study participants, the Institutional Review Board (IRB), and sponsor and will provide the reason(s) for the termination or suspension. Study participants will be contacted, as applicable, and be informed of changes to the study visit schedule.

Circumstances that may warrant termination or suspension include, but are not limited to:

- Determination of unexpected, significant, or unacceptable risk to participants
- Demonstration of efficacy that would warrant stopping
- Insufficient compliance to protocol requirements
- Data that are not sufficiently complete and/or evaluable
- Determination that the primary endpoint has been met
- Determination of futility

Study may resume once concerns about safety, protocol compliance, and data quality are addressed, and satisfy the sponsor, IRB and/or Food and Drug Administration (FDA).

In terminating the study, the Sponsor and the Principal Investigator will assure that adequate consideration is given to the protection of the subjects' interests.

10.1.3 Confidentiality and Privacy

Participant confidentiality and privacy is strictly held in trust by the participating investigators, their staff, and the sponsor(s) and their interventions. This confidentiality is extended to cover the clinical information relating to participants. Therefore, the study protocol, documentation, data, and all other information generated will be held in strict confidence. No information concerning the study or the data will be released to any unauthorized third party without prior written approval of the sponsor.

All discussions with potential participants, including by not limited to recruitment, consent discussion, and the study procedures will occur in private rooms behind closed doors within the emergency department.

The study monitor, other authorized representatives of the sponsor, representatives of the Institutional Review Board (IRB), regulatory agencies or pharmaceutical company supplying study product may inspect all documents and records required to be maintained by the investigator, including but not limited to, medical records (office, clinic, or hospital) and pharmacy records for the participants in this study. The clinical study site will permit access to such records.

The study participant's contact information will be securely stored at each clinical site for internal use during the study. At the end of the study, all records will continue to be kept in a secure location for as long a period as dictated by the reviewing IRB, Institutional policies, or sponsor requirements.

Study participant research data, which is for purposes of statistical analysis and scientific reporting, will be transmitted to and stored on REDCap. This will not include the participant's contact or identifying information. Rather, individual participants and their research data will be identified by a unique study identification number. The study data entry and study management systems used by clinical sites and research staff will be secured and password protected. At the end of the study, all study databases will be de-identified and archived on REDCap.

10.1.4 Future Use of Stored Specimens and Data

Data collected for this study will be analyzed and stored on REDCap. After the study is completed, the de-identified, archived data will be on REDCap for use by other researchers including those outside of the study. Permission to store data on REDCap will be included in the informed consent.

When the study is completed, access to study data and/or samples will be provided through REDCap.

10.1.5 Safety Oversight

Safety oversight will be under the direction of the PI and centralized monitoring group consisting of the Division of Ultrasound in the Department of Emergency Medicine. As this is a minimal risk study, a Data and Safety Monitoring Board is not planned for this study.

10.1.6 Clinical Monitoring

Clinical site monitoring is conducted to ensure that the rights and well-being of trial participants are protected, that the reported trial data are accurate, complete, and verifiable, and that the conduct of the trial is in compliance with the currently approved protocol/amendment(s), with International Conference on Harmonisation Good Clinical Practice (ICH GCP), and with applicable regulatory requirement(s).

- Centralized monitoring of this study will be completed by the Division of Ultrasound in the Department of Emergency Medicine, including a statistician, five faculty members, five fellows, and a research coordinator. The monitoring will occur once every two months and will consist of a random review of the data for verification of endpoint and safety.
- Independent audits may be conducted by the Office of Clinical Research at the University of Pennsylvania to ensure monitoring practices are performed consistently across all participating sites.

10.1.7 Quality Assurance and Quality Control

All monitoring and audits are to be performed according to ICH GCP E6(R2).

Each clinical site will perform internal quality management of study conduct, data and biological specimen collection, documentation and completion. An individualized quality management plan will be developed to describe a site's quality management.

Quality control (QC) procedures will be implemented beginning with the data entry system and data QC checks that will be run on the database will be generated. Any missing data or data anomalies will be communicated to the site(s) for clarification/resolution.

Following written Standard Operating Procedures (SOPs), the monitors will verify that the clinical trial is conducted and data are generated, and specimens are collected, documented (recorded), and reported in compliance with the protocol, International Conference on Harmonisation Good Clinical Practice (ICH GCP), and applicable regulatory requirements (e.g., Good Laboratory Practices (GLP), Good Manufacturing Practices (GMP)).

The investigational site will provide direct access to all trial related sites, source data/documents, and reports for the purpose of monitoring and auditing by the sponsor, and inspection by local and regulatory authorities.

10.1.8 Data Handling and Record Keeping

10.1.8.1 Data Collection and Management Responsibilities

Data collection is the responsibility of the clinical trial staff at the site under the supervision of the site investigator. The investigator is responsible for ensuring the accuracy, completeness, legibility, and timeliness of the data reported.

All source documents should be completed in REDCap and follow ALCOAC standards (attributable, legible, contemporaneous, original, accurate, and complete).

Clinical data (including adverse events (AEs), concomitant medications, and expected adverse reactions data) and clinical laboratory data will be entered into REDCap. The data system includes password protection and internal quality checks, such as automatic range checks, to identify data that appear inconsistent, incomplete, or inaccurate. Clinical data will be entered directly from the source documents.

10.1.8.2 Study Records Retention

Study documents should be retained for a minimum of 2 years after the last approval of a marketing application in an International Conference on Harmonization (ICH) region and until there are no pending or contemplated marketing applications in an ICH region or until at least 2 years have elapsed since the formal discontinuation of clinical development of the phrenic nerve block. These documents should be retained for a longer period, however, if required by local regulations. No records will be destroyed without the written consent of the sponsor, if applicable. It is the responsibility of the sponsor to inform the investigator when these documents no longer need to be retained.

10.1.9 Protocol Deviations

The PI and the study team should document all scenarios where the protocol is not followed and provide, in particular:

- Who deviated from the protocol
- What was the deviation
- When did the deviation occur
- How did the deviation happen
- What is the impact of the deviation
- A root cause analysis of why the deviation occurred

If the assessment results in a determination that any of the following are potentially affected, the deviation would be considered of significant impact:

- having the potential to adversely affect subject safety; OR

- increases risks to participants; OR
- adversely affects the integrity of the data; OR
- violates the rights and welfare of participants, OR
- affects the subject's willingness to participate in research.
- there is a potential for an overall impact on the research that should be shared with the IRB for consideration and development of next best steps to address it

